Considering the results of the above tests and non-clinical/clinical studies of similar products, it is deemed that similar PK profiles in animal testing predict similar PK profiles in humans as well. Therefore, since ISU304 and BeneFIX show similar PK profiles in animals, it may be predicted that they will show similar PK profiles in humans as well. Consolidating all results, it is expected that the intravenous administration of ISU304 (75 IU/kg) will show a PK profile similar to BeneFIX. This dose concentration is deemed to be safe as it falls within the approved range for BeneFIX (50 ~ 100 IU/kg) (Product Monograph for BeneFIX, 2012) and the normal range for humans (50 ~ 150 IU/dL).

[figure not shown]

Fig 1.1 The time-concentration curves of FIX in hemophilic mice and hemophilia patients
(A) The comparison of PK between ISU304 and BeneFIX in hemophilic mice, (B) The plasma concentration-time profile of 75 IU/kg rFIX (BeneFIX) intravenously administered to hemophilia patients (Lambert et al., 2009)

According to the clinical study data for BeneFIX reported in the above literature (Fig. 1.1 (B)), when 75 IU/kg of FIX is intravenously administered, C_{max} is approximately 55 IU/dL while AUC_{0-72h} is 851 ± 215 IU/dL*h, and blood concentration falls to 2.5 IU/dL 72 hours after administration (Fig 1.1(B): Lambert et al., 2009).

Blood concentration is expected to drop to 1 ~ 2%, 72 ~ 96 hours after a 75 IU/kg dose of ISU304 in this clinical study as well, similarly to BeneFIX. Thus, the blood collection period of 72 hours is deemed to be appropriate considering the subject's safety (Product Monograph for BeneFIX, 2012).

2) Single subcutaneous administration

As there is no commercially available rFIX protein product developed for subcutaneous administration, the initial subcutaneous doses in this clinical study have been set as 75, 150, and 300 IU/kg, based on animal testing results (on normal mice, hemophilic mice, hemophilic dogs and minipigs, etc.) obtained in the course of the development of ISU304, as well as results reported from a study on subcutaneous administration of FIX on humans.

The aspects of NOAEL, AUC and C_{max} have been considered in the initial doses and administration periods planned in this study, and the rationale for determination of the initial subcutaneous injection dose could be obtained as shown in .

Table 1.1.

Table 1.1 The rationale for Determination of Initial Subcutaneous Injection Dose

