4.4 Administration of Investigational Products and Follow Up Periods

- Cohort 1 (n=3) : 7 days
Single intravenous administration of BeneFIX (75 IU/kg) with 72 hours of observation, followed by single intravenous administration of ISU304 (75 IU/kg) with 72 hours of observation
- Cohort 2 (n=3) : 7 days
Single intravenous administration of ISU304 (75 IU/kg) with 72 hours of observation, followed by single subcutaneous administration of ISU304 (75 IU/kg) with 72 hours of observation
- Cohort 3 (n=3) : 9 days
Single intravenous administration of ISU304 (75 IU/kg) with 72 hours of observation, followed by single subcutaneous administration of ISU304 (150 IU/kg) with 120 hours of observation
-
- Cohort 4 (n=5) : 6 days
Single subcutaneous administration of ISU304 (150 IU/kg) per day for 6 days with 144 hours of observation
* At least 5 Subjects including the subjects from Cohorts 1 ~ 3 are expected to participate in Cohort 4.
- Cohort 5 (n=3~5) : 15 days
Single intravenous administration of ISU304 (75 IU/kg) is followed by subcutaneous ISU304 (150 IU/kg) administration for 9 days with 312 hours of observation

The baseline for all cohorts will be at the time before the intravenous or subcutaneous administration of the investigational products. Additional subjects may be enrolled in all cohorts or cohorts may be canceled depending on the results of PK/PD analysis. 14 days are allowed from the first

administration of the study drug to the second administration in cohorts 1 to 4 depending on the condition of subjects. If bleeding occurs 72 hours after first administration in cohorts 1 to 4 and FIX product is administered as a rescue medication, there must be at least of 4 days of wash-out period from the last administration of FIX.

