5.2.1.5 Visit 4 (Day 3 to 5) - 2nd Hospitalization

Visit 4 is for the 2nd administration of the study drug, and the subject is hospitalized for a day as in Visit 1. The subject is recommended to visit the hospital to be hospitalized on the day before the administration. The timing of the 2nd administration is also identical to the time that the subject will have to visit the hospital on subsequent visits. Thus the time of the 2nd administration should be determined with consideration for the subject's schedule.

An interval of at least 4 days is required between the administration of the 1st and 2nd doses. The investigator shall schedule the visit in consideration of this interval. Depending on the schedule, the procedure for Visits 3 and 4 could be conducted on the same day. Should this be the case, all procedures for the respective visits must be carried out without fail. The investigator must observe the administration site for at least 30 minutes to 1 hour after the administration of investigational product for AEs. The following is the procedure for Visit 4.

2nd hospitalization (Day 3 to 4)

- ① Hospitalization procedure for subject
- ② Checking for AEs and concomitant medications
- ③ Electrocardiogram
- ④ Blood/urine sample collection for laboratory tests, FIX inhibitor test, anti-drug antibody test, and Bethesda assay

2nd administration and blood collection for PK/PD analysis (Day 4)

- ① Checking for AEs and concomitant medications
- ② Physical examination, assessment of vital signs
- ③ Blood sample collection for PK/PD analysis before administration of investigational product
- ④ Administration of investigational product
For Cohort 1, ISU304 75 IU/kg, intravenous administration
For Cohort 2, ISU304 75 IU/kg, subcutaneous administration
- ⑤ Checking for AEs at least 30 min to 1 hr after investigational product administration
- ⑥ Blood sample collection for PK/PD analysis
For Cohort 1,
: 0(right after administration)hr±1min, 0.25hr±3min, 0.5hr±3min, 1hr±3min, 3hr±5min, 6hr±5min, 9hr±5min
For Cohort 2,
: 1hr±3min, 2hr±3min, 4hr±5min, 6hr±5min, 8hr±5min, 10hr±5min, 12hr±5min
- ⑦ Physical examination, assessment of vital signs, sample collection for blood coagulation test 6 hours after administration

2nd discharge (Day 5)

- ① Checking for AEs and concomitant medications
- ② Physical examination, assessment of vital signs
- ③ Blood sample collection for PK/PD analysis
24hr±15min

- ④ Sample collection for blood coagulation test

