8.2 Collection and Documentation of Adverse Events

AEs shall be collected during the clinical study period, from the time of investigational product administration to end of a cohort. Any medical incidences before the administration of the investigational product shall be recorded as current medical history.

AEs shall be reported with details on onset/end date, severity, outcome, action taken to investigational products, causal relationship with investigational products, causal relationship with other drugs, treatment given for AE, and seriousness. When documenting AEs, the investigators should record the overall diagnosis or symptoms using standard medical terms (according to the latest version of the MedDRA).

AEs occurring during the study period shall be followed up until recovery (or stabilization), or until the case is lost to follow up. AEs occurring after the study completion should be reported only when they are serious and causally related to investigational products.

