8.7 Other Statistical Considerations

The analysis will be carried out according to considerations as follows. If additional considerations on each analysis item is required, the corresponding options will be described in '10.1 Derivation'.

- In Cohort 1, Cohort 2, Cohort 3, 'Baseline' is '1st Hospitalization (Before 1st injection)' visit. And in Cohort 4 and Cohort 5, 'Baseline' is 'Before 1st injection' visit.
- The criteria for converting day to month are as follows: 1month=30days
- When calculating percentage for categorical variables except for 'Analysis Sets' summary, the denominator is the number of subjects in each cohort. Only in case of analysis by type of Medical History/Surgical History/Prior Medication/Concomitant Medication, the denominator is the number of subjects having Medical History/Surgical History/Prior Medication/Concomitant Medication in each cohort.
- The calculating criteria of percentage for 'Analysis Sets' summary will be described in 9.1 Disposition of Subjects'.
- The 95% confidence interval will be estimated by using exact method.

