9.5 Safety Evaluation

9.5.1 Adverse Events

The summary table for the following AE will be presented by each cohort. In the summary table, the number and proportion of subjects to whom following AE occurred, and its 95% confidence interval and the number of following AEs will be estimated.

- Adverse Event
- Adverse Drug Reaction^a
- Serious Adverse Event
- Serious Adverse Drug Reaction^a
- Early Withdrawal due to AE^b
- Adverse Event of Special Interest^c

^a Adverse Drug Reaction: AE including whose 'Causal Relationship with IP' is assessed "Definitely related", "Probably related", "Possibly related", "Unknown"

^b Early Withdrawal due to AE: AE whose 'Reason for discontinuation' of 'Study Conclusion' is

'Occurrence of an AE that leads treatment discontinuation' and 'Action taken to IP' is "Interrupted"
 c Adverse Event of Special Interest: It is Thrombosis/embolism, Spontaneous bleeding, Inhibitor generation/seroconversion, Anaphylaxis and collected in other AE only

Additionally, the summary table for the following local¹/systemic²/other³ AE will be presented by each cohort. In the summary table, the number and proportion of subjects to whom local/systemic/other AE occurred, and its 95% confidence interval and the number of following AEs will be estimated.

- Adverse Event
- Adverse Drug Reaction
- Serious Adverse Event
- Serious Adverse Drug Reaction
- Early Withdrawal due to AE

¹ Local AE: AEs occurring within 1 hour after the administration of investigational products including pain, tenderness, erythema/redness, urticaria/pruritus, and induration/swelling

² Systemic Adverse Event: AEs occurring within 1 hour after the administration of investigational products including fever, fatigue/malaise, chill/pyrexia, , headache, myalgia, arthritis(arthralgia), decreased appetite/loss of appetite, diarrhea, vomiting, constipation, abdominal pain, mucosal skin reaction/rash, vasovagal syncope, dizziness, cough, acute bronchospasm, dyspnea, and hypersensitivity

³ Other Adverse Event: AEs other than local or systemic AEs occurring after the administration of investigational products

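### Other AEs and spontaneous bleeds are reported as a proportion of subjects per cohort with no days of observation, although AE windows are unequal under either of the protocol's two AE-collection rules

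*Combined protocol and SAP*

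**What the plan says.** SAP 9.5.1 tabulates AEs, local/systemic/other AEs and AESIs by cohort as "the number and proportion of subjects to whom following AE occurred, and its 95% confidence interval", and adds that "the number of following AEs will be estimated". SAP 8.7 fixes the percentages and intervals: "the denominator is the number of subjects in each cohort" and "The 95% confidence interval will be estimated by using exact method". Neither section plans subject-days, a rate, or a split by dosing period.

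Spontaneous bleeding is an AESI, and SAP 9.5.1 places AESIs in the other-AE category. The one-hour limit that defines local and systemic AEs therefore does not apply, and bleeds accrue over the whole AE window.

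The protocol gives two ends to that window:

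- Section 8.2: "AEs shall be collected during the clinical study period, from the time of investigational product administration to end of a cohort". Footnote h to the synopsis schedule agrees.
- The last sentence of section 8.4.2 follows AEs not covered by the SUSAR rules for 14 days after the last dose. Section 5.2.6 adds an AE check at an optional visit 2 weeks (+1 week) after the end of the cohort.

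On the dose interval in Cohorts 1-3, section 5.2.1.5 states: "An interval of at least 4 days is required between the administration of the 1st and 2nd doses". Section 5.2.2.5 repeats this for Cohort 3. Section 4.4 allows 14 days from the first "administration of the study drug to the second administration in cohorts 1 to 4 depending on the condition of subjects". Only Cohorts 1-3 now have two separated doses, so the allowance is applied to them here.

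Section 4.4 also requires at least 4 days of wash-out if a bleed after 72 hours is treated with rescue FIX. Section 1.2.3 expects low activity by then: "Blood concentration is expected to drop to 1 ~ 2%, 72 ~ 96 hours after a 75 IU/kg dose of ISU304".

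**The concern.** Events that accrue with time show a higher proportion of affected subjects where follow-up is longer, even with identical safety. The by-cohort tables set these proportions side by side with exact intervals, and nothing on the page shows how long each cohort was observed.

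The dose gap in Cohorts 1-3 adds a second difficulty. Its length varies between subjects, and it falls when activity is expected to be about 1-2% or lower. Section 1.2.3 itself says that low FIX raises bleeding risk. A bleed in the gap still counts in the cohort's AESI row, beside bleeds soon after a dose. In Cohort 1 the gap follows BeneFIX, yet the bleed sits in the same row as ISU304 events. A rescued bleed can also lengthen that subject's own window through the wash-out. Cohorts 4-5 are dosed daily and have no such gap.

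**Working it through.** **1. The plan's own durations.** Window = day of last dose + observation after it.

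| Cohort | Last dose + observation | Scheduled window | Stated in synopsis | Stated in section 4.4 |
|---|---|---|---|---|
| 1, 2 | 4 + 3 (72 h; 5.2.1.7) | 7 d | 7 d | 7 d |
| 3 | 4 + 5 (120 h; 5.2.2.7) | 9 d | 9 d | 9 d |
| 4 | 5 + 5 (120 h; 5.2.3.6) | 10 d | 10 d | 6 d |
| 5 | 8 + 5 (120 h; 5.2.4.6) | 13 d (312 h / 24) | 15 d | 15 d |

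Four of the five synopsis durations reproduce. The 15 days for Cohort 5 does not match its own 312 hours, and section 4.4 contradicts the synopsis on Cohort 4.

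**2. Windows under each AE rule.**

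| Cohort | To end of cohort, dose 2 on day 4 | Same, dose 2 on day 14 | To 14 d after last dose |
|---|---|---|---|
| 1, 2 | 7 | 14 + 3 = 17 | 4 + 14 = 18 to 14 + 14 = 28 |
| 3 | 9 | 14 + 5 = 19 | 18 to 28 |
| 4 | 10 | n/a | 5 + 14 = 19 |
| 5 | 13 | n/a | 8 + 14 = 22 |

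Longest to shortest:

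- End-of-cohort rule: 13/7 = 1.9 as scheduled, and at most 19/7 = 2.7.
- 14-day rule: 22/18 = 1.2 as scheduled, and at most 28/18 = 1.6.

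**3. The gap in Cohorts 1-3.** Period 1 ends at 72 h (day 3), and dose 2 falls on days 4 to 14. The gap is 4 - 3 = 1 to 14 - 3 = 11 days. Check: 3 + (1 to 11) + 3 = 7 to 17, and 3 + (1 to 11) + 5 = 9 to 19. A bleed rescued on day 4 puts dose 2 no earlier than day 4 + 4 = 8. In Cohorts 1-2 that subject's window becomes at least 8 + 3 = 11 days instead of 7.

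**4. Subject-days (end-of-cohort rule).**

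- Cohorts 1 and 2: 3 x 7 = 21 to 3 x 17 = 51 each.
- Cohort 3: 3 x 9 = 27 to 3 x 19 = 57.
- Cohort 4: 5 x 10 = 50.
- Cohort 5: 3 x 13 = 39 to 5 x 13 = 65.

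**5. Illustration of size.** The documents give no event rate, so the rates below are assumptions. With a constant rate, P(at least one event) = 1 - exp(-rate x days / 365.25).

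| Assumed events per year | 7 d | 13 d | 19 d | 18 d | 22 d | 28 d |
|---|---|---|---|---|---|---|
| 2 | 3.8% | 6.9% | 9.9% | 9.4% | 11.3% | 14.2% |
| 6 | 10.9% | 19.2% | 26.8% | 25.6% | 30.3% | 36.9% |
| 12 | 20.5% | 34.8% | 46.4% | 44.6% | 51.5% | 60.1% |

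The first three columns belong to the end-of-cohort rule and the last three to the 14-day rule. A constant rate is a simplification, since bleeding risk depends on FIX activity.

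**6. Precision.** Exact 95% limits (Clopper-Pearson assumed) are 0-70.8% for 0/3, 0.8-90.6% for 1/3, 0-52.2% for 0/5 and 0.5-71.6% for 1/5. One event in 21 subject-days is 4.8 per 100 (exact Poisson 0.1-26.5); in 39 it is 2.6 (0.1-14.3).

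**The case against.** The strongest reply is that this is a small descriptive phase 1 study. No between-cohort test is planned, the intervals at n = 3 to 5 dwarf any distortion from window length, and 14 days is an allowance, not the schedule. Under the 14-day rule the scheduled windows differ by a factor of only 1.2. The SAP already lists every AESI and each patient's AEs, and dosing times are recorded, so a reader could place each bleed by hand.

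Most of this stands, and it limits the point to presentation. It does not remove it. The SAP text asks for no days at risk and no marker of gap time in those listings. The mock-up tables named in its appendix are not shown in the available text, so their columns cannot be checked. The headline table would still show bare proportions.

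A reader might infer more than the documents support:

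- **That escalation rests on distorted tables.** SAP 4.1 and 4.2 plan no interim analysis and produce these tables after database lock. Escalation follows committee review after each cohort (protocol 9.9).
- **That 10 further days come on top of 19.** The 19 days already include the delayed second dose.
- **That gap time is simply untreated background.** Section 4.4 provides for rescue FIX there, so follow-up may depend on the outcome, and a whole-cohort rate can be diluted by days the bleed created.
- **That the windows are settled.** They depend on which AE rule applies.

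**Conclusion.** The point holds as one of presentation and interpretation. Crude proportions of subjects with other AEs or AESIs are planned over windows that are unequal under both AE rules, with no denominator in days. Within Cohorts 1-3 the window also varies by subject, by up to 10 days. Time between the end of period 1 and dose 2 is not separated from post-dose time.

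Under the end-of-cohort rule, the assumed rates of 2 to 12 events per year give about 1.7 to 1.8 times the incidence at 13 days as at 7, and 2.3 to 2.6 times at 19 as at 7. Under the 14-day rule the contrast is smaller. These ratios rest on a constant assumed rate, and the upper figures need the full dose delay.

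The windows themselves are arithmetic from the visit schedule. The conflict between protocol 8.2 and 8.4.2 matters in its own right, because the SAP sets no end to the AE window.

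**What to change.** First, in the protocol:

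- Reconcile section 8.2 and synopsis footnote h with the last sentence of 8.4.2 and the AE check in 5.2.6, and state the single resulting window in SAP 9.5.1.
- Reconcile the durations of Cohort 4 (6 against 10 days) and Cohort 5 (15 days against 312 hours), and the reference to Cohort 4 in the 14-day allowance.

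Then, in SAP 9.5.1:

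- Keep the proportions. For other AEs and each AESI, add subject-days and events per 100 subject-days by cohort, with exact Poisson limits.
- For Cohorts 1-3, split days and events into post-dose observation (72 h, or 120 h after the Cohort 3 subcutaneous dose), the gap from the end of period 1 to dose 2, and any follow-up after the end of the cohort. Showing period 1 and period 2 separately also keeps BeneFIX time apart from ISU304 time in Cohort 1.
- In the AESI listing, flag gap bleeds and rescue FIX use.
- State a convention for events dated on a boundary day, because onset time is collected only for AESIs (protocol 5.1.15).

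The cost is SAP wording and one table. Dosing date and time (5.1.11), AE onset date (5.1.15, 8.2) and rescue drug use (2.3) are already recorded, so no new data or visits are needed for the end-of-cohort window. The downside is that rates from 3 to 5 subjects are very imprecise and should be labelled descriptive.

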6.1 Reasons for Withdrawal or Termination

Subjects may withdraw the informed consent or discontinue their participation in the clinical study at any time without specifying the reasons. The investigator or sponsor is also able to discontinue the clinical study of a subject for safety or administrative reasons. A subject may withdraw from the study in any of the following cases.

- Withdrawal of consent by the subject or the subject's representative
- Major protocol violations*
- Dispensing/dosing error of the investigational products
- Occurrence of an AE that leads to treatment discontinuation
- Follow-up loss
- Investigator or sponsor's decision that continuation of the clinical study is not appropriate
- Development of FIX inhibitor (confirmed by sponsor)

* Major protocol violations are defined as below.

- Failure to obtain informed consent (i.e., no documentation in source data or informed consent form)
- Violation of the inclusion/exclusion criteria
- Use of prohibited medication

For minor protocol violations which are not deemed to influence the analysis of study results, the degree of violation or delay shall be exactly mentioned, and when the clinical study result report is written, the investigator, sponsor, monitor, and biostatistician shall comprehensively evaluate the analysis.

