10.2 Categorization

Categories for each item are as follows.

The following defined category for continuous variable can be changed according to the distribution of actual collected data.

Item	Category
• Gender	Male
• Age	12 years ~ 19 years, 20 years ~ 29 years, 30 years ~ 39 years, 40 years ~ 49 years, 50 years ~ 59 years, 60 years ~ 65 years
• Duration of Hemophilia B	< Median, \geq Median (Median: median for Duration of Hemophilia B in Safety Analysis Set)
• Family History of	Yes, No

Item	Category
Hemophilia B	
• History of FIX Inhibitor	No
• Family History of FIX Inhibitor	No
• FIX activity \leq 2% before screening visit	Yes
• FIX product 150 exposure days at the time of screening	Yes
• Medical History	Yes, No
• Surgical History	Yes, No
• Prior Medication	Yes, No
• Concomitant Medication	Yes, No
• AE Seriousness	Yes, No
• AE Severity	Mild, Moderate, Severe
• AE Outcome	Recovered without Sequelae, Recovered with Sequelae, Continuing, Death, Unknown
• Action Taken to IP	Not Applicable, Interrupted
• Causal Relationship with IP	Definitely related, Probably related, Possibly related, Probably not related, Definitely not related, Unknown
• Causal Relationship with others	Concomitant Disease, Concomitant Medication, Other, Unknown, None

Item	Category
• Treatment Given for AE	None, Drug Therapy, Non-Drug Therapy, Drug, Non-Drug Therapy
• Laboratory Tests(Hematology test, Blood Chemistry test, Urinalysis, Blood coagulation test)	Normal/NCS, CS
• Laboratory Tests(Serology test)	Normal, NCS, CS
• Physical Examination	Normal/NCS, CS
• Electrocardiogram	Normal/NCS, CS

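### The SAP's two-condition definition leaves withdrawals coded to FIX inhibitor development, and possibly AE withdrawals after the last dose, out of the 'Early Withdrawal due to AE' row

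*Combined protocol and SAP*

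**What the plan says.** SAP 9.5.1 plans a summary table by cohort giving, for each AE category, the number and proportion of subjects, an exact 95% confidence interval and the number of events. One category is early withdrawal due to AE. It appears again in the local/systemic/other breakdown and in a listing of the AEs of those subjects.

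Footnote b defines the category. It opens with "Early Withdrawal due to AE: AE whose 'Reason for discontinuation' of 'Study Conclusion' is" and then requires the reason "Occurrence of an AE that leads treatment discontinuation" together with an action taken of 'Interrupted'. SAP 10.2 allows the action field two values only: "Not Applicable, Interrupted".

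Protocol 6.1 lists the reasons for withdrawal. One is "Occurrence of an AE that leads to treatment discontinuation". Another, listed separately, is "Development of FIX inhibitor (confirmed by sponsor". Footnote c of SAP 9.5.1 counts inhibitor generation among the AESIs: "Inhibitor generation/seroconversion, Anaphylaxis and collected in other AE only".

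Protocol 8.2 collects AEs "from the time of investigational product administration to end of a cohort", so collection continues after the last dose.

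**The concern.** Inhibitor development is an AE of special interest in this plan, and Protocol 2.1.3 names high-titer inhibitors among the most serious events known for the active control. A subject withdrawn for that event under its own protocol reason would still not count as an AE withdrawal in the safety table.

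The action condition raises a second, weaker problem. Once no dose remains, there is nothing to interrupt. If the site then records 'Not Applicable', a subject who leaves follow-up because of an AE fails the rule even when the AE reason is chosen.

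At stake is whether the AE-withdrawal row is right and whether it agrees with the disposition output. With three to five subjects per cohort, one case changes what the row says.

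**Working it through.** The plan states no figure on this point, so there is none to reproduce. The check is a reading of the rule, followed by the effect of one omitted case.

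**Step 1. Apply footnote b to each combination of reason and action.** The reasons come from Protocol 6.1 and the actions from SAP 10.2.

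| Study Conclusion reason | Action taken | In the row? |
|---|---|---|
| AE leading to treatment discontinuation | Interrupted | Yes |
| AE leading to treatment discontinuation | Not Applicable | No |
| FIX inhibitor | Interrupted | No |
| FIX inhibitor | Not Applicable | No |

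One of the four combinations counts. The inhibitor rows fail whatever the action field says.

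**Step 2. Can an inhibitor withdrawal occur before the cohort ends?** In Cohorts 1 to 3, yes. Protocol 5.2.1.4 and 5.2.2.4 test for inhibitors at the interim visit, before the second dose, and Protocol 4.4 allows up to 14 days between doses. In Cohorts 4 and 5 the scheduled post-dose inhibitor sample is taken at the end-of-study visit (Protocol 5.2.3.6 and 5.2.4.6), so a scheduled result would not prompt early withdrawal.

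**Step 3. How long is follow-up after the last dose?** It is 72 h in Cohorts 1 and 2 (Protocol 5.2.1.7) and 120 h in Cohorts 3 to 5 (Protocol 5.2.2.7, 5.2.3.6 and 5.2.4.6). AEs are still collected in this window. The documents do not say how the action field is completed for them.

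**Step 4. Effect of one omitted case.** Cohort sizes are 3 (Cohorts 1 to 3), 5 (Cohort 4) and 3 to 5 (Cohort 5). SAP 8.7 calls for an exact interval, which I take to be Clopper-Pearson: lower limit Beta(0.025; x, n−x+1), or 0 when x = 0; upper limit Beta(0.975; x+1, n−x). For x = 0 the upper limit is 1 − 0.025^(1/n).

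| n | One case counted (95% CI) | Same case omitted (95% CI) |
|---|---|---|
| 3 | 1/3 = 33.3% (0.8 to 90.6) | 0/3 = 0% (0 to 70.8) |
| 4 | 1/4 = 25.0% (0.6 to 80.6) | 0/4 = 0% (0 to 60.2) |
| 5 | 1/5 = 20.0% (0.5 to 71.6) | 0/5 = 0% (0 to 52.2) |

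These are illustrations. The documents give no withdrawal rate.

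**Step 5. Where do the cases still appear?** SAP 9.1 reports the number of early withdrawals with their reasons and lists the subjects. The AESI row and listing, the listing of AEs reported as positive for neutralizing or anti-drug antibodies, and the per-patient AE listing (all SAP 9.5.1) would show an inhibitor event recorded as an AE. SAP 9.5.6 tabulates and lists inhibitor results. The omission is therefore limited to the AE-withdrawal row, its repeat in the breakdown, and the matching listing if it uses the same definition.

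**The case against.** A reader might infer that these withdrawals are never counted. The documents do not support that, because the outputs in Step 5 still report them.

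A reader might also infer that every AE withdrawal after the last dose fails the rule. That depends on a coding convention the documents do not state. The protocol's AE reason is itself worded as leading to treatment discontinuation, so restricting the row to treatment discontinuation can be defended as a definition. Nor do the documents say that only one Study Conclusion reason may be chosen. An inhibitor case coded under the AE reason with 'Interrupted' would count.

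Post-dose follow-up is 38% to 56% of nominal observation time (120/312 h in Cohort 5, 120/216 h in Cohort 3). It is tempting to read this as the size of the problem. These are shares of time, not probabilities of a missed case, and the 14-day maximum interval lowers them to 72/408 = 18% in Cohorts 1 and 2 and 120/456 = 26% in Cohort 3.

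The best argument for footnote b is that the Study Conclusion reason belongs to the subject, while the row also counts events. The action field ties a particular AE to the discontinuation. The AE data items in Protocol 5.1.15 and 8.2 show no field for having caused withdrawal, so simply dropping the condition could count every AE of a withdrawn subject. This point stands and shapes the fix. Protocol 7.2.3.1 does not ask for an AE-withdrawal analysis, so the row is an SAP addition. That limits its weight but does not excuse a wrong count.

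**Conclusion.** The concern holds in a limited form. A withdrawal coded to the inhibitor reason is left out of the row by the stated rule, which does not depend on any unstated convention. A withdrawal for an AE after the last dose may be left out if the action is coded 'Not Applicable'. That the AE listing follows the same rule is an inference from its use of the same term.

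One omitted case moves a cohort from 20% to 33% down to zero. For an AE-reason withdrawal with action 'Not Applicable', the disposition figure would show an AE withdrawal while the safety table showed none. The effect is on descriptive safety reporting only, and no sample size or inferential result is involved. The likelihood of a case cannot be judged from the documents.

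**What to change.** Revise footnote b in two parts.

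- **Subject count:** take it from the Study Conclusion reason alone, accepting either the AE reason or the FIX inhibitor reason, whatever the action taken.
- **Event count and listing:** use only the AE linked to the withdrawal. That is the AE with action 'Interrupted'; for an inhibitor withdrawal, the inhibitor AESI; and where the action is 'Not Applicable', the AE identified from the Study Conclusion record. Unrelated AEs of the same subject then stay out.

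Apply the same definition to the local/systemic/other breakdown and to the listing, and state how the action field is coded for AEs after the last dose. The cost is a minor edit to the SAP and its program, plus some manual linking of AEs to withdrawals, which is small with cohorts of three to five.
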